2.3.1. Risk Assessment

Potential Risk of Clinical Significance	Summary of Data/Rationale for Risk	Mitigation Strategy
Study Intervention: IW-3300		
Potential for diarrhea and secondary dehydration	These are class effects of GC-C agonism or effects observed in nonclinical safety pharmacology and toxicology studies of IW-3300.	Intrarectal administration will likely decrease the risk of diarrhea and subsequent dehydration. The study design includes dose escalation to closely monitor subject safety and tolerability at each dose level before dosing with a higher dose; a Dose Escalation Committee will conduct blinded reviews of all the safety parameters of the dosing cohort through Discharge (Day 2) in order to make decisions regarding escalation to the next dose. Orthostatic vital sign measurements will be taken to evaluate the potential for volume depletion. The daily BM frequency and stool consistency will be monitored in real time to evaluate changes in bowel habits and the potential risk of diarrhea. Stopping rules will also be in place to evaluate continued dosing (Section 7.1.1); dosing within a cohort may be temporarily suspended in the event of a diarrhea or dehydration serious adverse event (SAE); ≥ 1 subject with Grade 3 diarrhea (increase from baseline of >7 stools per day and/or watery stools [BSFS score of 7] resulting in a limiting of self-care activities) or dehydration (hospitalization indicated); or ≥ 2 subjects with Grade 2 diarrhea (increase from baseline of 4 to 6 stools per day and/or watery stools [BSFS score of 7] resulting in a limiting of instrumental activities) or dehydration (intravenous fluids indicated).

Potential Risk of Clinical Significance	Summary of Data/Rationale for Risk	Mitigation Strategy

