8.2.2. Vital Signs

Vital signs will be performed as outlined in the SoA ([Table 1](#)).

- Oral temperature, pulse rate, and blood pressure will be assessed.
- Blood pressure and pulse measurements will be assessed with a completely automated device. Manual techniques will be used only if an automated device is not available.
- Blood pressure and pulse at 0.5 hours postdose on Day 1 will be assessed in a side-lying position (consistent with the position required following dosing).
- Blood pressure and pulse at the 2, 4, and 8 hour postdose timepoints should be preceded by at least 5 minutes of rest for the subject in a quiet setting without distractions (eg, television, cell phones).
- At all other timepoints, blood pressure and pulse measurements will be assessed in a supine and standing position (for calculation of orthostatic measurements). For orthostatic blood pressure and pulse measurements, the subject must lie quietly for ≥ 5 minutes before supine/semisupine blood pressure and pulse measurements are taken, then assume a standing position for 3 minutes before standing blood pressure and pulse measurements are taken. If a subject has orthostatic symptoms upon standing (eg, palpitation, dizziness), they will be assisted and asked to lie down without waiting the 3 minutes for vital sign assessment. At the discretion of the investigator, orthostatic measurements may be taken at other vital signs collection timepoints if clinically indicated.
- When applicable, vital signs measurements will be obtained immediately before blood draws.

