9. STATISTICAL CONSIDERATIONS

9.1. Statistical Hypotheses

No hypothesis testing is planned.

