4.1.1. Number of Subjects

A maximum of 40 subjects will be randomized in the study (up to 5 cohorts of 8 subjects each); within each cohort, 6 subjects will be randomized to IW-3300 and 2 subjects will be randomized to placebo.

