5.5. PD Analysis Set

The PD Analysis Set consists of all subjects in the Safety Analysis Set who have at least 1 postdose BBMD entry in the Clinic Period. Analysis will be performed according to the treatment actually received regardless of the allocated treatment.

All subjects on placebo arm will be pooled from available cohorts, whenever appropriate, to conduct analyses. All data will be summarized by cohort or treatment group, whenever it is appropriate.

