7.3. Vital Signs

Descriptive statistics for body weight and vital signs (ie, oral temperature, supine systolic and diastolic blood pressure, and pulse) and changes from baseline values at each time point will be presented by treatment group, and all the data will be listed. If there are multiple measurements for the same time point, the first one will be used for the by-time point analysis.

The number and percentage of subjects with PCS postbaseline vital signs will be tabulated by treatment group. A vital sign value will be considered PCS if it meets both the observed value criterion and the change from baseline criterion. The criteria for PCS vital sign values are detailed in [Table 3](#). The PCS percentages will be calculated relative to the number of subjects with baseline values and at least 1 assessment in the corresponding postbaseline period. The numerator will be the total number of subjects with available baseline values and at least 1 postbaseline PCS value.

A supportive data listing for subjects with PCS postbaseline values will be provided, including the subject ID number, baseline and postbaseline values for each visit, and a flag indicating the PCS vital sign values.

Table 3: Criteria for Potentially Clinically Significant Vital Signs

Vital Sign Parameter	Flag	Criteria ^a	
		Observed Value	Change from Baseline
Supine systolic blood pressure (mmHg)	High	≥180	Increase of ≥20
	Low	≤90	Decrease of ≥20
Supine diastolic blood pressure (mmHg)	High	≥105	Increase of ≥15
	Low	≤50	Decrease of ≥15
Supine pulse (beats per minute)	High	≥120	Increase of ≥15
	Low	≤50	Decrease of ≥15
Weight (kg)	High	-	Increase of ≥7%
	Low	-	Decrease of ≥7%

^a A postbaseline value is considered as a PCS value if it meets the criteria for both observed value and change from baseline.

In addition to supine measurements, at the predose measurement and at postdose time points 1, 6, and 24 hours, standing blood pressure and pulse will be measured 3 minutes after the supine measurements are taken. The standing blood pressure will be used to assess indicators of orthostatic hypotension. The criteria for testing positive for the orthostatic hypotension indicators are presented in [Table 4](#).

Table 4: Criteria for Orthostatic Hypotension Indicators

Blood Pressure Parameter	Change from Baseline
Supine systolic blood pressure (mmHg)	Increase of ≥20 mmHg
Supine diastolic blood pressure (mmHg)	Increase of ≥10 mmHg

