Subjects meeting either one of these two criteria are considered to be positive for indicators of orthostatic hypotension. The number and percent of subjects who are positive for these indicators will be tabulated by treatment group and by period (baseline versus postbaseline).

7.4. **Electrocardiogram**

TriPLICATE 12-lead ECGs will be obtained as outlined in the Schedule of Activities. An average of the 3 consecutive ECG values for each parameter (heart rate, PR interval, QRS interval, QT interval, and QTc interval), or 1 or 2 values if all 3 are not available, will be used for generating the summary statistics. Descriptive statistics for ECG parameters and their changes from baseline at each assessment time point will be presented by treatment group. QTc interval will be calculated using Fridericia correction ($QTcF=QT/(RR)^{1/3}$); if RR is not available, it will be replaced with 60/hr in the correction formula. ECG interpretation (designated as normal, abnormal not clinically significant, abnormal clinically significant) will be summarized by time point. A shift table from baseline to each visit for qualitative ECG results will be presented and all the data will be listed.

In addition, the number and percentage of subjects with PCS postbaseline ECG results will be tabulated by treatment group. An ECG value will be considered PCS if it meets the observed value criterion. The criteria for PCS ECG values are detailed in [Table 5](#). The percentages will be calculated relative to the number of subjects with available non-PCS baseline values and at least 1 postbaseline assessment. The potential numerator will be the total number of subjects with available non-PCS baseline values and at least 1 postbaseline PCS value in the corresponding postbaseline period.

A supportive data listing for subjects with PCS postbaseline values will be provided, including the subject ID number, baseline and postbaseline values for each visit, and a flag indicating the PCS ECG values.

Table 5: Criteria for Potentially Clinically Significant ECG Values

ECG Parameter	Unit	Higher Limit
QRS Interval	msec	≥ 150
PR Interval	msec	≥ 250
QTc Interval	msec	> 500

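### The postural blood pressure response is summarised only as a yes/no indicator over all postdose readings, so the size, timing and dose trend of any fall are lost

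*SAP*

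**What the plan says.** Protocol 2.3.1 gives the purpose of the readings in its row on diarrhea and secondary dehydration: "Orthostatic vital sign measurements will be taken to evaluate the potential for volume depletion". Protocol 8.2.2 says how they are taken. At every vital-sign time point other than 0.5, 2, 4 and 8 hours postdose, "blood pressure and pulse measurements will be assessed in a supine and standing position (for calculation of orthostatic measurements". Within the Clinic Period that means predose and 1, 6 and 24 hours after dosing.

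SAP 7.3 plans descriptive statistics and changes from baseline by time point for body weight and "vital signs (ie, oral temperature, supine systolic and diastolic blood pressure, and pulse". On the other position it says: "The standing blood pressure will be used to assess indicators of orthostatic hypotension". A subject who meets either the systolic (20 mmHg) or the diastolic (10 mmHg) criterion of Table 4 is positive, and "The number and percent of subjects who are positive for these indicators will be tabulated by treatment group and by period (baseline versus postbaseline". All vital-sign data are to be listed.

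Protocol 9.4.5 plans descriptive statistics and changes from baseline at each time point for systolic and diastolic pressure, without restricting them to one position. Neither document plans a summary of standing pressure or of standing minus supine.

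**The concern.** Diarrhea and secondary dehydration head the protocol's risk table, and the paired supine and standing readings are the check scheduled for volume depletion. The protocol collects the pairs so that an orthostatic measurement can be calculated. The SAP then keeps only whether a threshold was crossed, and merges the three postdose readings into one period. A fall that grows with dose, or that appears at 1 hour and is gone by 24 hours, cannot be seen in such a table.

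This also departs from the SAP's own practice. Numeric laboratory values, supine pressure and ECG intervals each get a continuous summary by time point as well as a threshold table. The postural response gets only the threshold, and no reason is given.

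**Working it through.** The plan has no figure to reproduce. The documents state no SD, effect size or power, and Protocol 9.1 says "No hypothesis testing is planned". What follows is an illustration.

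**Inputs from the documents.** Group sizes: "within each cohort, 6 subjects will be randomized to IW-3300 and 2 subjects will be randomized to placebo" (SAP 4.1.1). Placebo: "All subjects on placebo arm will be pooled from available cohorts, whenever appropriate, to conduct analyses" (SAP 5.5; Protocol 9.4.1 is similar). Four cohorts give 4 × 2 = 8 placebo subjects, or 10 with optional Cohort 5. There are three postdose pairs: 1, 6 and 24 h.

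**Assumptions.**
- Standing minus supine averages -2 mmHg systolic and +3 mmHg diastolic without drug.
- Systolic between/within-subject SD is 4/5, 5/6 or 6/8 mmHg; diastolic SDs are 0.7 times these, with deviations independent of systolic.
- The diastolic drug effect is half the systolic effect.
- The indicator is read as a standing fall of at least 20 mmHg systolic or 10 mmHg diastolic at any of the three postdose readings.
- A two-sided 0.05 level is a yardstick for separation, not a proposed test.

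**Continuous difference, one time point.** For each subject take the postdose difference minus the predose difference. The between-subject part cancels.
- SD of change = √2 × within-subject SD = 7.07, 8.49, 11.31 mmHg.
- SE of active minus placebo = SD × √(1/6 + 1/8) = SD × 0.540 = 3.82, 4.58, 6.11 mmHg.
- For an 8 mmHg fall, 8/SE = 2.10, 1.75, 1.31. Noncentral t power on 12 df is 48.7%, 36.2%, 22.6%. Simulating the same model gives about 49%, 36% and 22%.
- 95% interval half-width = 2.179 × SE = 8.3, 10.0, 13.3 mmHg.

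**Indicator.** The chance that a subject is positive was simulated under the assumptions above. Separation is the exact power of Fisher's test, 6 against 8.
- Placebo: 0.0123, 0.0525, 0.170.
- Active, 8 mmHg at all three readings: 0.197, 0.326, 0.500, giving power 1.5%, 6.5%, 12.4%.
- Active, 8 mmHg at one reading only: 0.086, 0.168, 0.311, giving power 0.1%, 0.6%, 2.3%.

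The reason is visible in the counts. With 0 of 8 placebo subjects positive, 3 of 6 active gives p = 0.055 and 4 of 6 gives p = 0.015.

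| Extra systolic fall | Difference, one time point | Indicator, fall at all three | Indicator, fall at one |
|---|---|---|---|
| 5 mmHg | 23 / 17 / 12% | 0.1 / 0.8 / 4% | 0 / 0.1 / 1% |
| 8 mmHg | 49 / 36 / 23% | 2 / 6 / 12% | 0.1 / 0.6 / 2% |
| 10 mmHg | 67 / 52 / 33% | 8 / 18 / 23% | 0.5 / 2 / 4% |

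Each cell is in SD order 4/5, 5/6, 6/8.

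**Wider SDs.** With an SD of 8 to 12 mmHg for the difference itself at one time point, not adjusted for predose, and a 10 mmHg fall, the difference separates the groups in 30 to 57% of trials. Over a comparable range of assumptions the indicator does so in 3 to 23% (fall at all three readings) or 0.3 to 5% (one reading).

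**Chance of any positive subject.** For a sustained 10 mmHg fall the chance per active subject is 0.316, 0.444, 0.599, so at least one of 6 is positive in 1 - (1 - p)^6 = 90%, 97% and over 99% of trials. At least one of 8 placebo subjects is positive in 1 - (1 - p)^8 = 9%, 35% and 77%.

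**The case against.** The strongest reply is that the indicator is not blind. A reader might infer that a real postural fall will usually not show in the table. The documents do not support that, and the calculation contradicts it for larger falls: a sustained 10 mmHg fall flags at least one active subject in 90% or more of trials. What the count does poorly is tell such subjects apart from placebo subjects, who may be flagged too.

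A reader might also expect a larger gain by averaging the three postdose differences: about 65%, 50% and 31% at 8 mmHg. That figure needs a fall held constant from 1 to 24 hours after a single dose, which no document states. If the fall is present at one reading only, the average gives 12%, 10% and 8%. The summary proposed here is by time point, so those higher figures do not apply to it. In turn, the by-time-point figures refer to a time point at which the fall is present, and with three time points a reader has three looks.

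Other replies stand in part:
- No test is planned, every SD is assumed, and some of the gap reflects the conservatism of Fisher's test at these group sizes.
- Six subjects limit the difference as well: a 5 mmHg fall would mostly be missed on either scale.
- The raw values are listed, and weight, supine pressure, pulse, laboratory values, stool data and adverse events also bear on volume depletion. Dose escalation rests on blinded review of all safety and tolerability parameters, not on this table. A reader should therefore not conclude that volume depletion would go unexamined.

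None of this supplies the missing summary. A listing of up to 40 subjects does not give a group mean, its spread or a dose trend.

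**Conclusion.** The point holds as a gap in the planned summaries. The postural difference is reduced to a positive/negative count over 1, 6 and 24 hours, and the difference itself is never summarised, although the protocol takes both positions in order to calculate it. That follows from the text and needs no assumption.

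The cost in sensitivity depends on assumed SDs, effect sizes and a reading of Table 4 as a standing fall. In every non-zero scenario shown, the by-time-point difference separated active from pooled placebo better than the count. At 8 mmHg the advantage was roughly 10 to 47 percentage points for a sustained fall (22.6 - 12.4 and 48.7 - 1.5) and 20 to 49 for a fall at one reading (22.6 - 2.3 and 48.7 - 0.1). The percentages illustrate the direction and rough scale and do not predict this trial. The change is worth making because it is cheap and concerns a risk the protocol names, but it does not undermine the study.

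Table 4 labels its criteria as increases in supine pressure from baseline, while the text refers to standing pressure. That is a separate matter and the two must be reconciled. Settling it would still leave only a yes/no count.

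**What to change.** In SAP 7.3:

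- Derive standing minus supine systolic and diastolic pressure at predose and at 1, 6 and 24 hours postdose.
- Present descriptive statistics of this difference, and of its change from the predose difference, at each time point by dose group and pooled placebo, with the difference from pooled placebo.
- Keep the indicator table as a supplement.

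The cost is a few lines of SAP wording and one extra descriptive table. The readings are already scheduled, so no new measurement or protocol amendment is needed, and no hypothesis test has to be added.

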7. SAFETY ANALYSIS

All safety parameters will be summarized using descriptive statistics. Safety analyses will be performed on the Safety Analysis Set. The safety parameters will include AEs, clinical laboratory evaluations, vital signs, and ECGs. For each laboratory parameters and ECG site interpretation, the last nonmissing assessment before the first dose of study drug will be used as the baseline for all analyses of that laboratory parameter or ECG interpretation. For numeric ECG measurements, the average of the last triplicate ECG before dosing will be used as baseline. For vital signs, the last supine measurement before dosing will be used as baseline.

All safety analyses will be performed according to the treatment actually received regardless of the allocated treatment.

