^a Subjects will be discharged on Day 2 unless they have physical examination findings or laboratory abnormalities that are considered by the investigator to be clinically meaningful. In the event that a subject discontinues from the study, an early termination visit will be performed prior to discharge from the CRU. The early termination assessments will be the same as those conducted at Discharge (Day 2). Every effort should be made and documented to ensure that safety procedures scheduled for Discharge are performed at the early termination visit.

^b Height will only be measured at the Screening Visit. At Check-in (Day -1) and Discharge (Day 2), subjects will be weighed in the morning upon awakening and before they ingest any water or food.

^c Rectal examination should be performed at each physical examination; the rectal examination at all timepoints should include a digital rectal examination and inspection of the perianal area for redness or irritation.

^d Vital signs will include oral temperature, blood pressure, and pulse rate. Side-lying blood pressure and pulse will be obtained at the 0.5 hour postdose timepoint on Day 1 (consistent with the position required following dosing). Blood pressure and pulse at the 2, 4, and 8 hour postdose timepoints should be preceded by at least 5 minutes of rest for the subject in a quiet setting without distractions (eg, television, cell phones). At all other timepoints (ie, predose and 1, 6, and 24 hours postdose), orthostatic blood pressure and pulse measurements will be obtained; subject must lie quietly for ≥5 minutes before supine/semisupine blood pressure and pulse measurements are taken, then assume standing position for 3 minutes before standing blood pressure and pulse measurements are taken. If a subject has orthostatic symptoms upon standing (eg, palpitation, dizziness), they will be assisted and asked to lie down without waiting the 3 minutes for vital sign assessment. Orthostatic measurements may be taken at other vital signs collection timepoints if clinically indicated, at the discretion of the investigator. When applicable, vital sign measurements will be obtained immediately before blood draws.

^e ECGs should be obtained after the subject has been supine for at least 5 minutes. At each timepoint required, 3 individual ECG tracings should be obtained as closely as possible in succession, but no more than 2 minutes apart. The full set of triplicates should be completed in less than 4 minutes.

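### SAP Table 4 flags orthostatic hypotension by a rise in supine pressure, although the text above it says standing pressure will be used

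*SAP*

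**What the plan says.** SAP 7.3 plans standing blood pressure and pulse at predose and at 1, 6 and 24 h postdose, and gives their purpose: "The standing blood pressure will be used to assess indicators of orthostatic hypotension". It then refers to Table 4 for the criteria. Both rows of Table 4 name supine pressure, under a header that refers to change from baseline. The systolic criterion is "Increase of ≥20 mmHg" and the diastolic criterion is "Increase of ≥10 mmHg". Meeting either one is enough, and the count of positive subjects "will be tabulated by treatment group and by period (baseline versus postbaseline").

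The baseline is defined in SAP section 7: "For vital signs, the last supine measurement before dosing will be used as baseline". The other blood pressure summaries in SAP 7.3 are also supine. The descriptive statistics cover "oral temperature, supine systolic and diastolic blood pressure, and pulse", and the Table 3 blood pressure and pulse criteria are labelled supine.

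Protocol 8.2.2 has pressures taken at the orthostatic time points "in a supine and standing position (for calculation of orthostatic measurements"). Protocol 2.3.1 gives the reason, which is to look for volume depletion. Footnote d of the Schedule of Activities in SAP 12.3 allows extra readings: "Orthostatic measurements may be taken at other vital signs collection timepoints if clinically indicated, at the discretion of the investigator".

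**The concern.** Table 4 departs from its own lead-in and title on two elements and leaves a third open.

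- **Position.** The lead-in says standing; both rows say supine.
- **Direction.** The title says hypotension; both criteria are rises.
- **Reference.** The header points to the predose supine baseline. Protocol 8.2.2 implies the supine reading paired with each standing reading, but the SAP does not say so.

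If the table is programmed as written, it reports rises in resting pressure under the title of orthostatic hypotension. Diarrhea with secondary dehydration is the first risk listed in protocol 2.3.1, and orthostatic readings are among its mitigations. The one summary meant to show those readings would then say nothing about them.

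**Working it through.** The plan gives no figure to reproduce. The check codes the rule as written, compares it with a rule that uses the standing reading, and tests partial corrections.

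**Rules.** Let U be supine and S standing pressure, t a postdose time point and 0 predose. Each rule needs only one of its two conditions.

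- Literal Table 4: U(t) − U(0) ≥ 20 systolic or ≥ 10 diastolic.
- Paired: S(t) − U(t) ≤ −20 systolic or ≤ −10 diastolic.

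The literal rule has no S term. Varying the standing value from 60 to 180 systolic and from 40 to 120 diastolic never changed the flag. In the baseline period the literal change is U(0) − U(0) = 0, so under that reading the baseline column is zero by construction.

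**Worked cases** (invented pressures, mmHg; case 3 applies the fall in case 1 to the supine readings in case 2):

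| | Case 1 | Case 2 | Case 3 |
|---|---|---|---|
| U(0) | 120/75 | 110/70 | 110/70 |
| U(1 h) | 118/74 | 131/76 | 131/76 |
| S(1 h) | 93/60 | 128/77 | 106/62 |
| Literal, U(1 h) − U(0) | −2/−1: no flag | +21/+6: flag | +21/+6: flag |
| Paired, S(1 h) − U(1 h) | −25/−14: flag | −3/+1: no flag | −25/−14: flag |
| S(1 h) − U(0) | −27/−15 | +18/+7 | −4/−8 |

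**Partial corrections.**

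- Changing only supine to standing asks whether S − U(0) is a rise of 20/10. In case 1 it is −27/−15, so the subject is still missed.
- Changing only the direction asks whether U(t) − U(0) is a fall of 20/10. In case 1 it is −2/−1, so the subject is again missed.
- Changing both but keeping the predose supine reference flags case 1 but misses case 3, where the change is −4/−8 although the fall on standing is 25/14. The reference therefore has to be stated too.

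**Illustrative flag rates.** The documents give no SDs, correlations or fall sizes, so every input here is an assumption:

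- independent readings, with reading SD equal to change SD/√2;
- systolic-diastolic correlation 0.5;
- three postdose time points;
- a true fall that shifts standing readings only;
- 400,000 simulated subjects per setting.

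| Change SD (systolic/diastolic) | 6/5 | 8/6 | 10/7 | 12/8 |
|---|---|---|---|---|
| Literal, no fall | 0.058 | 0.123 | 0.202 | 0.284 |
| Literal, fall 20/10 | 0.059 | 0.122 | 0.203 | 0.285 |
| Literal, fall 40/20 | 0.058 | 0.122 | 0.203 | 0.284 |
| Paired, no fall | 0.067 | 0.147 | 0.247 | 0.351 |
| Paired, fall 20/10 | 0.963 | 0.963 | 0.963 | 0.963 |
| Paired, fall 40/20 | 1.000 | 1.000 | 1.000 | 1.000 |
| Position changed only, no fall | 0.059 | 0.123 | 0.203 | 0.283 |
| Position changed only, fall 20/10 | 0.000 | 0.001 | 0.006 | 0.018 |

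With a true fall of 20/10, the literal rule misses 94%, 87%, 79% and 71% of subjects with a measured fall. With only the position changed, the flag becomes rarer when there is a real fall.

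The constant 0.963 comes from placing the fall exactly at the cut-off. At one time point the chance of meeting neither criterion is then 1/4 + arcsin(0.5)/(2π) = 1/3, whatever the SD. Over three independent time points the flag rate is 1 − (1/3)³ = 26/27.

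**The case against.** The strongest reply is that nobody would program the table as written. The lead-in sentence, the title and the baseline-versus-postbaseline layout all point to a comparison within a time point. A charitable reading, that supine exceeds standing by 20/10, leaves only the header and the row labels at fault. That may well be what was meant. But the SAP does not say it, and case 3 shows that two plausible repairs classify the same subject differently. The SAP introduction says analysis decisions are made before database lock and unblinding, so the rule should be written down.

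A second reply is that little depends on the table, and this largely stands. Dose escalation rests on the Dose Escalation Committee's blinded review, which includes vital signs. Vital-sign changes that the investigator judges clinically significant are reported as adverse events. No hypothesis is tested, and all vital-sign data are listed.

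A third reply is that the simulation follows from its assumptions, which is also fair. The flat literal rate results from letting the fall affect standing readings only, whereas volume depletion could lower supine pressure too. The paired rate at a 20/10 fall drops from 0.963 to about 0.89, 0.77 and 0.67 if the correlation between time points is 0.5, 0.9 and 1.0. Nothing in Table 4 limits a supine rule to 1, 6 and 24 h; six independent postdose readings would give literal rates of about 0.10 to 0.41. The worked cases do not depend on any of this.

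**Conclusion.** The concern holds. Table 4 contradicts its lead-in sentence on position and its title on direction, and the SAP leaves the reference reading open. No other section of either document supplies a standing rule. That the literal criterion contains no standing reading follows from the text alone. The simulated rates (literal 0.06 to 0.28 regardless of the true fall; paired 0.07 to 0.35 with no fall and 0.96 at 20/10) only illustrate scale under assumed inputs.

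This should be fixed, but it does not threaten the trial's conclusions. It affects a supportive descriptive table, with the raw readings still available in the listings.

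**What to change.** Before database lock, the sponsor should confirm what Table 4 was meant to measure and reconcile it with the sentence above it. If a fall on standing was intended, then, keeping the SAP's own figures:

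- Define a positive as standing minus supine at the same time point of ≤ -20 mmHg systolic or ≤ -10 mmHg diastolic.
- Evaluate it at predose for the baseline column and at 1, 6 and 24 h for the postbaseline column.
- Replace the column header with *Standing minus supine, same time point*.
- State whether extra, clinically indicated orthostatic readings count in the postbaseline column or are shown separately.

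Two further sentences would be useful. One would state the denominator and how the table treats subjects who lie down with symptoms before the 3-minute standing reading. The other would confirm that a semisupine reading, which protocol 8.2.2 allows, serves as the supine member of the pair.

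The cost is two table rows, one header and a few sentences. The paired readings at predose, 1, 6 and 24 h are already scheduled, so no new data are needed.

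### The orthostatic table sets one predose stand against three or more postdose stands with no stated rule for combining them, so the within-group rise from baseline cannot be read as a drug effect

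*SAP*

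**What the plan says.** SAP 7.3 schedules the stands: "at the predose measurement and at postdose time points 1, 6, and 24 hours, standing blood pressure and pulse will be measured". Protocol 8.2.2 adds that "orthostatic measurements may be taken at other vital signs collection timepoints if clinically indicated", and the footnotes to the schedule in SAP 12.3 repeat this.

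For classification, "Subjects meeting either one of these two criteria are considered to be positive for indicators of orthostatic hypotension". The two criteria are in Table 4. Its rows are labelled supine systolic and supine diastolic pressure, its column is change from baseline, and the systolic entry is "Increase of ≥20 mmHg" (10 mmHg for diastolic). The sentence introducing the table says that standing pressure is what is assessed.

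The output is a count and percentage: "subjects who are positive for these indicators will be tabulated by treatment group and by period (baseline versus postbaseline"). No rule says how several postdose stands are reduced to one result per subject. The closest rule, for potentially clinically significant (PCS) vital signs in the same section, is "The numerator will be the total number of subjects with available baseline values and at least 1 postbaseline PCS value".

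The time-point summaries in SAP 7.3 are for supine pressure and pulse. Protocol 9.4.5 promises blood pressure summaries by time point without naming a position. All vital-sign data are listed.

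**The concern.** Protocol 2.3.1 names diarrhea with secondary dehydration as a risk and relies on orthostatic readings to pick up volume loss. The indicator table is the only orthostatic tabulation that the SAP specifies.

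Its two columns do not give a subject the same number of chances to be positive. If one positive stand is enough, a subject has one chance before dosing and at least three after it. A higher postbaseline percentage is then expected from the counting alone. In dose groups of 6, one or two such positives could be misread as volume depletion caused by the drug.

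Collapsing the postdose period also loses timing. A positive at 1 h, after about an hour lying down and still fasted, need not mean the same as one at 6 or 24 h.

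**Working it through.** The documents state no orthostatic rate, so there is no figure to reproduce. The check is what the table would show with no drug effect.

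**Inputs from the documents**
- Scheduled stands: 1 predose, 3 postdose (SAP 7.3). The wording of Protocol 8.2.2 could also cover a Screening stand, but SAP 7 fixes a single baseline reading: "For vital signs, the last supine measurement before dosing will be used as baseline".
- Group sizes: 6 active and 2 placebo per cohort (SAP 4.1.1). Pooled placebo (SAP 5.5) is 4 × 2 = 8, or 5 × 2 = 10 with the optional cohort.

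**Assumptions, not in the documents**
- A chance-positive rate p per stand, the same at every stand, from 2% to 20%.
- A subject is positive postbaseline if any of the three scheduled stands is positive.
- Within-subject latent correlation ρ of 0, 0.5 or 0.9 (one-factor probit model).

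**Formula.** For independent stands, P(any of 3) = 1 − (1 − p)³. At p = 5%: 1 − 0.95³ = 1 − 0.857 = 14.3%. For correlated stands, 1 − (1 − q(x))³ is averaged over a standard normal x, with q(x) = Φ[(Φ⁻¹(p) − √ρ·x)/√(1 − ρ)].

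| Baseline, one stand (p) | Any of 3, ρ = 0 | ρ = 0.5 | ρ = 0.9 |
|---|---|---|---|
| 2% | 5.9% | 5.1% | 3.4% |
| 5% | 14.3% | 11.8% | 8.0% |
| 10% | 27.1% | 21.8% | 15.0% |
| 20% | 48.8% | 38.9% | 27.9% |

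The ratio to baseline runs from about 1.4 (27.9/20) to 2.9 (5.9/2). It reaches 1 only if a subject's repeat stands always agree.

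**In a dose group of 6, at p = 5%**
- Expected positives, independent stands: 6 × 0.05 = 0.30 at baseline, 6 × 0.143 = 0.86 postbaseline.
- Chance of at least one positive: 1 − 0.95⁶ = 26.5% at baseline; 1 − 0.857⁶ = 60.3% postbaseline (53.0% at ρ = 0.5).

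**In pooled placebo of 8, at p = 5%**
- Expected positives, independent stands: 8 × 0.05 = 0.40 at baseline, 8 × 0.143 = 1.14 postbaseline. The proportional rise is the same as on active, so the expected active-minus-placebo difference is 14.3% − 14.3% = 0.
- Chance of no postbaseline positive: 0.857⁸ = 29% (36% at ρ = 0.5).

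**By time point.** Each row is one stand, so with equal p the expected rate is p in every row and the artificial rise is 0.

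**Table 4 as printed.** The predose supine reading is the baseline, so its change from baseline is 0 and the baseline column is zero by construction. A rise in supine pressure is also not a fall on standing. The figures above apply only once positivity is defined from supine and standing readings at the same time point.

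**The case against.** The strongest answer is the control group. The table is split by treatment group, placebo subjects have the same scheduled stands, and pooling gives 8 to 10 of them. A reader might infer that the table falsely shows drug-induced volume depletion. The documents do not support that: for scheduled stands, active versus placebo is unbiased. This stands, with two limits. Placebo is small enough to show no positive by chance, and stands added for symptoms could differ between groups.

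Three other strong readings also fail.
- That the SAP counts any positive stand: this is inferred from the PCS rule and is not written for this indicator. The firm finding is the missing rule.
- That every group will show a rise: it is an expectation only, and eight placebo subjects may well show no positive.
- That the one-versus-three effect holds under any blood pressure criterion: it does not operate under Table 4 read literally.

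A reader might also argue that subjects positive predose must be excluded, because the laboratory and ECG PCS rules restrict to normal baselines. The vital-sign PCS rule in SAP 7.3 has no such restriction, so the SAP sets no uniform standard, and exclusion would shrink groups of 6.

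The stakes are limited too. No hypothesis test is planned (Protocol 9.1), escalation rests on blinded cohort review that includes vital signs (Protocol 6), and the listings let the timing of a positive be recovered.

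**Conclusion.** The point holds in a limited form. The baseline and postbaseline columns rest on unequal numbers of stands, and the SAP omits the rule for combining them. On the natural any-positive reading, the within-group percentage is expected to rise with no drug effect: from an assumed 5% to about 8% to 14% for ρ from 0.9 to 0, and by a factor of about 1.4 to 2.9 over the whole range examined. The size rests on an assumed rate and correlation. The direction rests on the any-positive rule, on a working same-time-point definition, and on a per-stand rate that is the same before and after dosing.

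Only the baseline-to-postbaseline reading within a group is affected. This is a cheap improvement to a descriptive safety table, and it depends on Table 4 being corrected first.

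**What to change.** In SAP 7.3:
1. Reconcile Table 4 with its introductory text, so that positivity is defined from the supine and standing readings at the same time point.
2. Replace the split by period with a tabulation by scheduled time point (predose, 1, 6 and 24 h) and treatment group.
3. If an any-postdose row is kept, state the combination rule, show unscheduled stands separately, and interpret the row against pooled placebo rather than against baseline.
4. Say which reading counts when one is repeated at a time point: SAP 7.3 takes the first and SAP 12.1.2 the last.

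The cost is a short SAP revision and a new table shell. No new data are needed. The downside is a few more sparse rows, and splitting by time point does not stop one or two chance positives from being over-read in groups of 6. If the per-stand rate differs by time of day or after an hour lying down, placebo at the same time point remains the proper comparator.
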